11.2.4. Serious Adverse Event

An AE or SAR is considered "serious" if, in the view of the PI or Sponsor, it results in any of the following outcomes (see 21 CFR 312.32(a)):

- ***Death***: Includes all deaths, even those that appear to be completely unrelated to study drug (e.g. a car accident in which a subject is a passenger)
- ***A life-threatening event***: In the view of the investigator, the subject is at immediate risk of death at the time of the event. This does not include an AE that had it occurred in a more severe form, might have caused death.
- ***In-patient hospitalization or prolongation of existing hospitalization*** (excludes hospitalization for continued observation of allergic reaction for potential of biphasic reaction). In-subject hospitalization is defined as admission to a hospital or an emergency room for longer than 24 hours. Prolongation of existing hospitalization is defined as a

hospital stay that is longer than was originally anticipated for the event, or is prolonged due to the development of a new AE as determined by the investigator or treating clinician.

- **Persistent or significant disability/incapacity** (substantial disruption of one's ability to conduct normal life functions)
- **Congenital anomaly/birth defect**
- **Important medical events** that may not result in death, be life threatening, or require hospitalization may be considered serious when, based upon appropriate medical judgment, they may jeopardize the participant and may require medical or surgical intervention to prevent one of the outcomes listed above

Elective or pre-planned hospitalizations for a pre-existing condition or hospital admissions for the purposes of conducting protocol mandated procedures are not considered to be an SAE unless prolonged due to complications.

Injectable epinephrine may be used for both life threatening and non-life threatening allergic reactions. The use of epinephrine will not be considered an SAE if it is used to prevent the progression of non-life-threatening allergic reactions that occur during OFCs (see Section 7.4).

11.2.5. Adverse Events of Special Interest

An adverse event of special interest (AESI; serious or non-serious) is one of scientific and medical concern specific to the sponsor's product or program, for which ongoing monitoring and rapid communication by the investigator to the sponsor can be appropriate. Such an event might warrant further investigation in order to characterize and understand it. Depending on the nature of the event, rapid communication by the trial sponsor to other parties (e.g. regulators) might also be warranted.

AESIs for dupilumab or placebo in this study include the following:

- Life threatening anaphylactic reactions
- Systemic or extensive hypersensitivity reactions
- Malignancy
- Helminthic infections
- Suicide-related events
- Conjunctivitis (any type or etiology), keratitis or blepharitis (for all these AEs only events that are severe or serious or lasting ≥ 4 weeks will be reported as AESIs)

AESIs for milk OIT in this study include:

- Life threatening Anaphylactic reactions
- Gastrointestinal AEs resulting in prolonged disruption of dosing; gastrointestinal AEs include dysphagia, nausea, vomiting, abdominal pain, diarrhea, but exclude oral itching/tingling.

11.2.6. Anaphylaxis

The definition of anaphylaxis that has been adopted for this study is from the 2014 position paper by the European Academy of Allergy and Clinical Immunology (EAACI) Food Allergy and Anaphylaxis Guidelines Group ([Muraro 2007](#)), that was based on the publications of Simons

et al. (2011) and Johansson et al. (2004), and is consistent with the recently published “International consensus on (ICON) anaphylaxis” (Simons 2014). Accordingly, anaphylaxis is defined as a severe, potentially life-threatening systemic hypersensitivity reaction, characterized by being rapid in onset with life-threatening airway, breathing, or circulatory problems that is usually, though not always, associated with skin and mucosal changes.

Clinical criteria for diagnosing anaphylaxis will be as follows (Sampson 2006):

Anaphylaxis is likely when any one of the 3 following sets of criteria is fulfilled:

1. Acute onset of an illness (minutes to several hours) with involvement of skin and/or mucosal tissue (e.g. generalized hives, pruritis or flushing, swollen lips/tongue/uvula) AND at least one of the following:

- Respiratory compromise (eg, dyspnea, stridor, wheeze/ bronchospasm, hypoxia, reduced PEF)
- Reduced blood pressure (BP) or associated symptoms of end-organ dysfunction (e.g. hypotonia, syncope, incontinence)

2. Two or more of the following that occur rapidly after exposure to a likely allergen for that patient (minutes to several hours):

- Involvement of the skin/mucosal tissue (e.g. generalized hives, itch/flush, swollen lips/tongue/uvula)
- Respiratory compromise (e.g. dyspnea, stridor wheeze/bronchospasm, hypoxia, reduced PEF)
- Reduced BP or associated symptoms (e.g. hypotonia, syncope, incontinence)
- Persistent GI symptoms (e.g. vomiting, crampy abdominal pain)

3. Reduced BP after exposure to the allergen (minutes to several hours):

- Infants and Children: Low systolic BP* (age-specific) or >30% drop in systolic BP
- Adults: Systolic BP <90 mm Hg or >30% drop from their baseline

**Low systolic BP for children is defined as less than (70 mmHg + [2 x age]) from 1 to 10 years; and <90 mmHg from age 11 to 17 years*

With respect to the inclusion of being “potentially life-threatening” in the definition of anaphylaxis and how that relates to the assessment of anaphylaxis as an SAE, reference is made to the 2012 FDA Guidance for Industry and Investigators, “Safety Reporting Requirements for INDs and BA/BE Studies,” that states, “An adverse event or suspected adverse reaction is considered “life-threatening” if, in the view of either the investigator or sponsor, its occurrence places the subject or subject at immediate risk of death. It does not include an adverse event or SAR that, had it occurred in a more severe form, might have caused death.” Thus, for the reporting of anaphylaxis as an SAE, the severity of the reaction, assessed according to the EAACI system for grading the severity of anaphylactic reactions (Muraro 2007), is also to be taken into account (see **Table 5**).

When the diagnosis of anaphylaxis is made, the basis for having suspected the diagnosis must be documented, using the criteria detailed above.

11.3. Grading and Attribution of Adverse Events

11.3.1. Grading Criteria

The study site will grade the severity of all allergic and non-allergic adverse events, experienced by the study subjects according to the criteria set forth in the National Cancer Institute's Common Terminology Criteria for Adverse Events (CTCAE) Version 5.0. This document (referred to herein as the NCI-CTCAE manual) provides a common language to describe levels of severity, to analyze and interpret data, and to articulate the clinical significance of all adverse events. The NCI-CTCAE has been reviewed by the Principal Investigator and has been deemed appropriate for the subject population to be studied in this protocol. For additional information and a printable version of the NCI-CTCAE manual, consult the NCI-CTCAE web site:

https://ctep.cancer.gov/protocoldevelopment/electronic_applications/docs/CTCAE_v5_Quick_Reference_5x7.pdf

Adverse events will be graded on a scale from 1 to 5 according to the following standards in the NCI-CTCAE manual Events Grade 1 or higher will be recorded on the appropriate AE paper CRF for this study.

Grade 1 = mild adverse event

Grade 2 = moderate adverse event

Grade 3 = severe and undesirable adverse event

Grade 4 = life-threatening or disabling adverse event

Grade 5 = death

In the case that the diagnosis of anaphylaxis is made, the severity of the anaphylactic event will be assessed and staged according to the EAACI system for grading the severity of anaphylactic reactions ([Muraro 2007](#)) detailed in **Table 5**.

Table 5. Criteria for Grading of Anaphylaxis Severity

Staging System of Severity of Anaphylaxis	
Stage	Defined By
1. Mild (skin & subcutaneous tissues, GI, &/or mild respiratory)	Flushing, urticaria, periorbital or facial angioedema; mild dyspnea, wheeze or upper respiratory symptoms; mild abdominal pain and/or emesis
2. Moderate (mild symptoms + features suggesting moderate respiratory, cardiovascular or GI)	Marked dysphagia, hoarseness and/or stridor; shortness of breath, wheezing & retractions; crampy abdominal pain, recurrent vomiting and/or diarrhea; and/or mild dizziness
3. Severe (hypoxia, hypotension, or neurological compromise) (i.e. Life threatening)	Cyanosis or SpO ₂ ≤ 92% at any stage, hypotension, confusion, collapse, loss of consciousness; or incontinence

For grading an abnormal value or result of a clinical or laboratory evaluation (including, but not limited to, a radiograph, an ultrasound, an electrocardiogram, etc.), a treatment-emergent adverse event (TEAE) is defined as an increase in grade from baseline or from the last post-baseline value that does not meet grading criteria. Changes in grade from screening to baseline will also be recorded as AEs but are not treatment-emergent. If a specific event or result from a given clinical or laboratory evaluation is not included in the NCI-CTCAE manual, then an abnormal result would be considered an AE if changes in therapy or monitoring are implemented as a result of the event/result.

11.3.2. Attribution

The relationship, or attribution, of an AE to the study therapy regimen or study procedures will be determined by the investigator(s) based on all available information and recorded on the appropriate AE/SAE CRF. Final determination of attribution for safety reporting will be determined by the Sponsor.

Table 6. Attribution of Adverse Events

Category	Descriptor	Relationship (to Study Drug or Procedure)
UNRELATED CATEGORY	Not Related	The AE is clearly not related; there is insufficient evidence to suggest a causal relationship.
RELATED CATEGORIES	Possible	The AE has a reasonable possibility to be related; there is evidence to suggest a causal relationship.
	Definite	The AE is clearly related.

11.4. Collection and Recording of Adverse Events

11.4.1. Collection Period

AEs will be collected from the time of consent until a participant completes study participation or until 30 days after he/she prematurely withdraws (without withdrawing consent) or is withdrawn from the study. Ongoing AEs at the time of study completion will be followed for 30 days or until the time of resolution, whichever occurs first. SAE information will be collected until the event is considered chronic and/or stable.

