The immune system in the gut actively induces an immune tolerant state to the proteins that are normally consumed. Food allergy occurs when the body has a break in this tolerance, which results in an abnormal immune reaction to food. Milk allergy is an IgE-mediated hypersensitivity reaction following the ingestion of normally innocuous milk protein. Cross-linking of milk-specific IgE (sIgE) bound to high affinity IgE receptors on mast cells and basophils triggers immediate degranulation, and the subsequent release of a diverse array of inflammatory mediators results in severe allergic symptoms such as hives, wheezing, vomiting and, in severe cases, anaphylactic shock. Release of these mediators also initiates type 2 helper T-cell (Th2) cytokine release, which results in eosinophil infiltration and creates a vicious cycle of chronic allergic inflammation. Like other forms of allergy immunotherapy, OIT to milk involves a slow up-dosing of exposure to allergen over time to desensitize or increase the threshold of reactivity to milk. Once reaching a target level of milk protein, subjects are continued on a maintenance dose of milk protein to maintain desensitization. Although many subjects on a maintenance dose of milk protein have demonstrated desensitization to milk (i.e. the ability to tolerate a level of exposure to milk without an allergic reaction), up to 95% subjects exhibit related adverse events (AEs) during OIT with 40% experiencing gastrointestinal (GI) symptoms ([Vázquez-Ortiz 2013](#), [Martorell Calatayud 2014](#), [Mori 2017](#), [De Schryver 2019](#)). While the majority of these are mild and decline with prolonged treatment, approximately 25% of patients experience more severe, unpredictable reactions. Roughly 20 to 30% of patients are unable to complete their up-dosing regimen due to side effects, of which the majority are related to the GI system. In those who do successfully desensitize, an additional issue with current OIT arises, specifically its limited ability to induce clinical tolerance (i.e. the persistence of desensitization after subjects are taken off of OIT) ([Keet 2012](#), [Suárez-Fariñas 2019](#)). In many of the studies with milk OIT, despite years of

immunotherapy, subjects lose their tolerance within weeks of halting daily milk intake, with only 50% or fewer patients maintaining a sustained unresponsiveness after 2 months off OIT.

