3.6.1. Blinding

Placebo control and randomization will be the main methods to minimize bias in this trial. DBPCFCs will be performed during screening, at week 18 and at week 24. During the DBPCFC, the order of the milk and placebo (oat) challenges will be chosen at random by the unblinded pharmacy personnel, and both the patient and study staff will be blinded to the randomized order of the challenges. Milk powder and its placebo (oat) are both off-white, dry powders and should be difficult to differentiate unless directly compared side by side. An unblinded pharmacist or dietitian designee will mix the milk protein or oat in a food vehicle selected to aid in masking the taste and appearance of the food challenge doses prior to their dispensation for administration in the DBPCFC. To the extent practicable, the same blinded evaluating clinician who determines dose limiting symptoms in the screening DBPCFCs for a participant should evaluate the symptoms in week 18 and 24 DBPCFCs.

Dupilumab and placebo matching dupilumab will be labeled for research purposes in such a way that maintains the blind. Both the active product and placebo are identical in appearance.

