Participants will return to clinic 2 weeks (± 5 days) from Visit 11a for Visit 12, and again in two weeks (± 5 days) for Visit 13. Visits 12 and 13 will be conducted in the same fashion and include all procedures as Visits 4 to 10 listed above, excluding administration of dupilumab/placebo. All participants not yet tolerating 1000 mg daily milk protein will continue to attempt dose escalations in clinic at each visit until a maximum daily dose of 1000 mg protein, as tolerated. Those escalating to and tolerating a daily dose of 1000 mg protein daily will remain at that dose for the remaining visits. The final possible up-dosing will occur at Visit 13.

Week 24 Double-Blind, Placebo-Controlled Food Challenge (Visits 14a and 14b)

At week 24, all subjects will undergo DBPCFCs up to 4040 mg milk protein (cumulative) and placebo to assess desensitization. The DBPCFCs will occur at two separate visits within the span of 10 days. Randomization of the placebo and milk challenge order and preparation of the challenge materials will be performed by trained unblinded study personnel. Both milk protein and oat will be concealed in an age-appropriate, non-offensive food vehicle that aids in masking the taste and appearance.

At Visit 14a, participants will return unused OIT doses remaining from the previously dispensed home dosing kit. Prior to the DBPCFC, accountability will be performed on the returned doses, when able, and the Daily Dosing & Symptom Diary will be reviewed to assess for AEs and home dosing compliance. Additionally, prior to the first dose of the Visit 14a DBPCFC, a blood draw will be performed and a stool/saliva sample will be collected (optional).

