As detailed above, the subject will have a physical examination and lung function assessment conducted to ensure it is safe and appropriate to proceed with the escalation. All food challenges will be performed under clinician supervision. Vital signs will be assessed every 15 minutes. The DBPCFC will consist of 7 doses (milk protein or placebo), given every 15 to 30 minutes: 10 mg, 30 mg, 100 mg, 300 mg, 600 mg, 1000 mg, and 2000 mg protein, resulting in a total challenge of up to 4040 mg milk protein (cumulative). If the study team suspects a reaction may be developing, they may exercise their clinical judgment to separate doses by up to an additional 30 minutes (1 hour maximum between doses). The food challenge will be stopped and appropriately treated in the occurrence of two or more objective Grade 1 (Mild) reactions involving two or more organ systems; OR a persistent Grade 1 (Mild) reaction; OR any reaction of Grade 2 (Moderate) or higher severity. After the last dose of each DBPCFC, the subject will be monitored for a minimum of 2 hours and then discharged from the clinic only when deemed clinically stable by a study clinician. The food challenges can be performed on consecutive days if no reactions have occurred. If a reaction occurs and is treated, then the challenges should be at least 48 hours apart.

Participants will be discharged with a new kit of home OIT doses at Visit 14a at the same dose as that previously dispensed and tolerated at Visit 13. Participants will skip their daily home dose of milk OIT on DBPCFC days (Visit 14a and b), but will take their home dose on days between the DBPCFCs if the DBPCFCs are not on consecutive days. At Visit 14b, participants will return unused OIT doses remaining from the home dosing kit dispensed at Visit 14a. Accountability will be performed on the returned doses, when able, and the Daily Dosing & Symptom Diary will be reviewed to assess for AEs and home dosing compliance.

The conclusion of the second DBPCFC and Visit 14b will mark study completion for each participant. Participants can exit the trial at Visit 14b to meet the study completion criteria.

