11.2. Definitions

11.2.1. Adverse Event

Any untoward or unfavorable medical occurrence associated with the use of an intervention in humans, whether or not considered related to the intervention (see 21 CFR 312.32(a)). An AE can be any unfavorable and unintended sign, symptom, or disease temporally associated with the use of a drug, and does not imply any judgment about causality. An AE also includes any worsening (i.e. any clinically significant change in frequency and/or intensity) of a pre-existing condition that is temporally associated with the use of the study drug.

All symptoms or events that occur within two hours and that are expected according to the Investigator's Brochure (milk OIT), package insert (dupilumab), or protocol and related to administration of study drug or oral food challenge will be recorded as a dosing reaction, not an AE; however, episodes in response to home dosing that are Grade 3 or higher per CTCAE V5.0 criteria or that are classified as serious adverse events (SAEs) per **Section 11.2.4.** below, will be recorded on the AE/SAE case report form (CRF) as appropriate.

Any symptom or event that occurs more than two hours after study dosing will be recorded as an AE on the AE CRF but will not be identified as a dosing reaction.

For this study, an AE will include any untoward or unfavorable medical occurrence associated with:

Study therapy regimens:

Dupilumab/Placebo for Dupilumab
In-clinic OIT dosing
Home OIT Dosing

For the study-mandated procedures below, only the signs and symptoms listed under each procedure will be considered outside normal range and will be recorded as an AE. For all other study-mandated procedures, all AEs will be recorded.

Skin Prick Test

The following events related to SPT will be considered AEs if they occur within 48 hours of the SPT:

- Prolonged (>24 hours) pruritus at the SPT site
- Induration/swelling at the SPT site larger than 10 mm in diameter and lasting more than 24 hours
- Allergic or anaphylactic reaction that requires the use of rescue medications, detailed in **Section 7.2**

Blood Draw

The following events related to a blood draw procedure will be considered AEs:

- Syncope/vasovagal events within 30 minutes of the procedure
- Bleeding from the puncture site lasting more than 30 minutes
- Bruising at the puncture site >5 cm in diameter within 24 hours of procedure
- Erythema at the puncture site >5 cm in diameter within 24 hours of procedure

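### Completers whose last milk challenge falls at Visit 14b have no scheduled collection of new adverse events after discharge

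*Combined protocol and SAP*

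**What the plan says.** All references are to the combined protocol and SAP.

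- **Collection window (11.4.1).** "AEs will be collected from the time of consent until a participant completes study participation or until 30 days after he/she prematurely withdraws". The 30-day extension does not apply to participants who withdraw consent. AEs still present at completion are followed for up to 30 days. The SAE sentences in 11.4.1 and 11.4.3 say how long an SAE is followed, but give no window for a new SAE after completion.
- **When a participant completes (8.3).** "The conclusion of the second DBPCFC and Visit 14b will mark study completion for each participant". The section adds: "Participants can exit the trial at Visit 14b to meet the study completion criteria". Visit 14b is the last column of Table 4.
- **The two week 24 challenges (8.3 and 3.6.1).** "The DBPCFCs will occur at two separate visits within the span of 10 days", and "the order of the milk and placebo (oat) challenges will be chosen at random by the unblinded pharmacy personnel". The milk session goes up to 4040 mg cumulative protein. Observation after the last dose lasts at least 2 hours, and discharge requires that a clinician judges the participant stable.
- **Late events (11.2.1).** "Any symptom or event that occurs more than two hours after study dosing will be recorded as an AE on the AE CRF". Section 11.2.6 describes anaphylaxis with onset ranging from minutes to several hours after exposure.

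**The concern.** Read together, these sections end the collection of new AEs at the visit where some completers have just received the largest single-session milk exposure in the trial. The plan itself classes a reaction that starts more than two hours after dosing as an AE, yet schedules nothing to find one after Visit 14b. Whether a delayed reaction to the same challenge is asked about therefore depends on which session happened to contain milk.

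At stake is the completeness of the safety data. Safety is part of the primary objective (2.2) and AE rates are secondary endpoints (3.5.2). The study stopping rules (10.3) count hypotension and severe anaphylaxis related to food challenges, and those counts depend on events being collected.

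**Working it through.** **1. The plan's own sample size (13.2), which supplies the number of completers.** Inputs are 20% vs 55%, two-sided 5%, Fisher exact test. Exact enumeration gives 90.8% power at 44 per arm, so the stated 90% is reproduced. For drop-out, 44 / 0.75 = 58.7; the plan enrols 58 per arm, 116 in all. The difference from 59 is immaterial, and nothing in this point affects power.

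**2. Completers with the milk challenge at Visit 14b.** Number = 116 × (1 − drop-out) × share with milk second.

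- The 25% drop-out in 13.2 sizes the week 18 analysis. Using it for completion at week 24 is an assumption.
- The documents give no ratio for challenge order. An even split is an assumption.
- 116 × 0.75 = 87 completers, and 87 × 0.5 = 43.5. The binomial 95% range is 34 to 53.
- With 40% to 60% having milk second: 34.8 to 52.2.
- With an even order and drop-out of 10% to 30%: 52.2 to 40.6.

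These are people exposed, not events missed. The documents give no rate of reactions that start after discharge. If that rate were 1%, 5% or 10% (assumed), the expected number among 43.5 people would be 0.4, 2.2 or 4.4.

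**3. What follows each milk challenge.**

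| Milk challenge at | Next scheduled AE review |
|---|---|
| Week 18 (Visit 11a or 11b) | Visit 11b or Visit 12 |
| Visit 14a | Visit 14b, up to 10 days later |
| Visit 14b | None |

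The 30-day follow-up of ongoing AEs does not fill the last row. It covers events already present. Under 11.2.1 an expected reaction within two hours is logged as a dosing reaction, not an AE, so a recurrence at home after that reaction has settled is not clearly covered.

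**4. Does the 30-day difference bias the arms?** A participant withdrawn at week w has 7w + 30 days of collection from week 0, against 168 for a completer. The two are equal at w = 138 / 7 = 19.7, so only late withdrawals have more. For illustration, assume 35% drop-out on placebo and 15% on dupilumab, all at week 10 (70 + 30 = 100 days):

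- Current rule, placebo: 20.3 × 100 + 37.7 × 168 = 8,364 person-days.
- Current rule, dupilumab: 8.7 × 100 + 49.3 × 168 = 9,152 person-days. Gap 789.
- With 30 days added for completers (198 days each): 9,495 vs 10,631. Gap 1,137.

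In this example the present rule narrows the difference in total collection time between arms.

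**The case against.** The strongest reply is that the gap is narrow and partly covered. Two hours is a minimum, and discharge depends on clinical stability. Participants have a 24-hour emergency number (5.5), unsolicited complaints are an accepted source of AEs (11.4.2), and investigators must report every SAE and AESI within 24 hours of learning of it, with no cut-off stated for completers (11.5). All of this stands. A reader might infer that late reactions at Visit 14b are never collected or cannot enter the database, but the documents do not say that. What is missing is any scheduled enquiry and any stated window. The routes listed are passive, so the gap remains.

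A reader might also infer that the longer follow-up of withdrawals biases the AE comparison between arms. The documents do not support this. Withdrawals usually lose more in-study time than the 30 days return, as the example shows. Section 13.6.1 plans numbers and percentages of subjects, not person-time rates. Challenge order is random in both arms, so missed late reactions are not obviously differential.

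Finally, the Background (1.1) says that in many milk OIT studies "subjects lose their tolerance within weeks of halting daily milk intake". That statement concerns how long desensitization lasts. It does not identify a post-trial AE risk that this study set out to follow, and the point does not rest on it.

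**Conclusion.** The point holds as a limited gap in safety capture. The stated rule, followed as written, leaves roughly 43 to 44 of 87 completers without planned collection of new-onset reactions once they leave Visit 14b. That figure depends on the assumed 25% drop-out at week 24 and an even challenge order. How many reactions would be missed cannot be derived from the documents.

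A related mismatch should be settled at the same time. Section 13.6.1 runs the treatment period to study end, which Section 3.2 defines as the last subject's last visit, while 11.4.1 stops collection participant by participant. The primary endpoint and power are unaffected, and no between-arm bias is established. This is an inexpensive improvement, not a threat to the trial's conclusions.

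**What to change.** - **11.4.1:** extend collection of new AEs, AESIs and SAEs for completers to a stated point after Visit 14b, for example 30 days, to match withdrawals. For everyone else keep at least the present window by using the later of study exit plus 30 days and last exposure plus 30 days. A rule based on last exposure alone could shorten collection for participants who stop treatment but keep attending visits (6.5.2), or who are withdrawn after a run of missed OIT doses (10.1).
- **Table 4:** add a telephone contact within 24 to 72 hours of Visit 14b. A call at day 30 is optional; without it, the later part of the window relies on participants reporting events themselves.
- **13.6.1:** define the treatment period per participant so that it ends with this collection window.

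The cost is amendment wording, one short call per completer (about 87 on the assumptions above), and final safety data up to about 30 days later. No visit, procedure or treatment rule changes.
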